11.4 Secondary Efficacy Analysis: WHO-7 Ordinal Scale

11.4.1 Time to first improvement of one category from baseline on WHO-7

The time to first improvement of one category on WHO-7 scale from baseline (Days) is defined as:

Date of First Improvement on Ordinal Scale – Date of Baseline Assessment + 1.

If the patient did not experience an improvement, the patient will be censored at the last known date the patient is known to not have experienced an improvement:

Final Date of Confirmation of No Improvement - Date of Baseline Assessment + 1.

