**Table 3 Schedule of Events**

Trial Activity	Screening/Baseline/ Enrolment visit	Daily until hospital discharge	End of treatment	Follow-up period	
Day	1	2-14	15	29	60
Allowed window for visit (±)	-1 a		2	2	3
Visit	1		2 b	3	4
Informed consent	•				
Inclusion/exclusion criteria including confirmation of COVID-19 diagnosis	•				
Confirmation SARS-CoV-2 h	•	•	•	•	
Pregnancy test	•				
Demographics/Medical History	•				
Physical Exam	•				
Vital signs c	•	•	•	•	
Clinical support data collection f	•	•	•	•	
Safety Laboratory Testing d	•	•	•	•	
Cytokine Markers k	•	•	•		
Child-Pugh Score i	•	•			
PaO 2 and PaO 2 /FiO 2 ratio j	•	•	•	•	
ECG	•				
Cough Severity (VAS) e	•	•	•	•	
Extent of Dyspnea (Likert Scale) e	•	•	•	•	
Adverse Events documented	•	•	•	•	•
Concomitant Medications	•	•	•	•	
Randomization	•				
Administer IP	•	•			
Vital Status					• g

a Screening/baseline may occur up to 24 hours prior to randomization

b Treatment can be given up to 14 days post randomization, or until hospital discharge, whichever comes first. If patient is discharged prior to Day 14, the next visit should be Visit 2.

c Includes blood pressure (measured after the patient has been in a seated position (if possible) for ≥3 minutes of rest), pulse, respiratory rate, body temperature, and SpO2. Body weight and height will be measured at the screening visit only.

d Baseline, Days 3, 5, 8, 11 if hospitalized, Day 15, Day 29

e Baseline, Days 2, 4, 8, and 14 if hospitalized, Day 15 (if not done Day 14), Day 29

f Includes NEW Score, on Baseline, Days 3, 5, 8, 11 if hospitalized, Day 15, Day 29

g Vital status (is patient alive)

h Baseline, Days 5 (or discharge, whichever comes first) and 15. Day 29 for subjects with viral RNA detected at Day 15.

Qualitative (mandatory) and Quantitative (if available) testing done all days.

i Baseline, Days 3, 5, 8, 11 if hospitalized

j Minimum complete baseline, Days 3, 5, 8, 11, 15 and 29. If PaO2 not able to be taken, SpO2 should be obtained using a forehead sensor. Fingertip probes may be used if forehead sensors are not available. Remain consistent with the method of testing for the patient over the course of the study.

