### 7.3.2 Daily Assessments (Days 2 - 14; Treatment Period)

At each study day while hospitalized, the following data will be collected:

- Vital signs (including pulse, respirations rate, body temperature, systolic and diastolic blood pressure, SpO2)
- Assess measures of clinical support
  - Hospitalized
  - Oxygen requirement
  - Non-invasive mechanical ventilation (via mask)
  - Mechanical ventilator requirement (via endotracheal tube or tracheostomy tube)
  - ECMO requirement
  - Ordinal Scale Assessment
  - The ordinal scale is an assessment of the clinical status at the first assessment of a given study day. Each day, the worse score for the previous day will be recorded. i.e. on Day 3, Day 2 score is obtained and recorded as Day 2. The scale is as follows:
    1. Not hospitalized, no limitations on activities
    2. Not hospitalized, limitation on activities
    3. Hospitalized, not requiring supplemental oxygen
    4. Hospitalized, requiring supplemental oxygen
    5. Hospitalized, on non-invasive ventilation or high flow oxygen devices
    6. Hospitalized, on invasive mechanical ventilation or ECMO
    7. Death
  - NEW Score (Days 3, 5, 8, 11 if still hospitalized)
- SARS-CoV-2 RNA status testing (Day 5, or discharge, whichever comes first)
- Safety laboratory testing (Days 3, 5, 8, 11 if still hospitalized)
- Child-Pugh Score (Days 3, 5, 8, 11 if still hospitalized)
- Cytokine Markers (Day 5)
- PaO2 and PaO2/FiO2 ratio
- VAS score questionnaire (Days 2, 4, 8, and 14 if still hospitalized)
- Extent of Dyspnea (Likert Scale, Days 2, 4, 8, and 14 if still hospitalized)
- Adverse Events recorded
- Concomitant medications
- IP administration (daily until discharge or Day 14)

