2.3.2 Secondary endpoints

- Status on an ordinal scale assessed daily while hospitalized and on days 15 and 28 in IP versus control group patients
- NEWS assessed days 3, 5, 8, 11 while hospitalized and on days 15 and 29 in IP versus control group patients
- Rate of mechanical ventilation in IP versus control group patients
- Duration of mechanical ventilation (if applicable) in IP versus control group patients
- Duration of supplemental oxygen in IP versus control group patients
- Time to return to SpO₂ > 94% on room air
- Duration in ICU (if applicable) in IP versus control group patients
- Rate of Mortality in IP versus control group patients
- Duration of hospitalization in IP versus control group patients
- Time to discharge in IP versus control group patients
- Effect on the rate of change of partial pressure of oxygen (PaO₂) and PaO₂/FiO₂ ratio taken at baseline and measured once daily up to 2 weeks of treatment in IP versus control group patients

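### Time to one-category improvement has no rule for discharge alive, so some early recoveries would be dated at about Day 15

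*SAP*

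**What the plan says.** SAP 11.4.1 measures time from baseline to the "Date of First Improvement on Ordinal Scale". A patient without improvement is censored at the "Final Date of Confirmation of No Improvement". Discharge appears in neither rule.

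The scores come from Protocol 7.3.2 for Days 2 to 14: "At each study day while hospitalized, the following data will be collected". On what is recorded, the same section says "Each day, the worse score for the previous day will be recorded", with the example that the Day 2 score is obtained on Day 3. For a patient who leaves early, Protocol Table 3, footnote b, says "If patient is discharged prior to Day 14, the next visit should be Visit 2", which is Day 15 ±2. SAP 2.3.2 describes the same pattern: "Status on an ordinal scale assessed daily while hospitalized and on days 15 and 28" (the visit schedule has Day 29 for the last of these).

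Four other rules matter:
- SAP 3.3 has data analysed as collected, with no imputation unless stated.
- SAP 11.1 carries a score of 7 forward after death. It is the only fill-in rule for WHO-7.
- Protocol 5.1 admits patients at category 4 or 5. Categories 1 and 2 are the two non-hospitalized categories.
- SAP 11.5.1 counts discharge as an event for the NEWS endpoint, and SAP 11.8.2 uses the discharge date for time to discharge.

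**The concern.** Everyone discharged alive has improved by at least two categories, on a date the trial collects. If the event is dated from recorded scores, part of this information is lost. A patient who stops oxygen and leaves at once has a last inpatient score of 4, and the next score may be more than a week later. A true early event then becomes a late one at Visit 2.

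SAP 11.3 reports Kaplan-Meier medians, plots and Cox hazard ratios for endpoints of this kind. Events moved to one visit day shift the medians late and create many ties. Protocol 4.1 and SAP 2.1 say that Phase 2b data will be used to select and rank the secondary endpoints for Phase 3, so an endpoint with distorted event dates could be ranked wrongly.

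**Working it through.** The documents give no median, event count or power for this endpoint, so there is no planned figure to reproduce.

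**Step 1: apply the recording rule day by day.** The score for day k is the worst of day k and is recorded on day k+1 if the patient is still in hospital. Take a baseline of 4 with oxygen stopped on Day 5. The worst score for Day 5 is still 4. The first score of 3 belongs to Day 6 and is recorded on Day 7.

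| Discharged on | Dated as written | Dated with discharge counted | Difference |
|---|---|---|---|
| Day 5 | Day 15 | Day 5 | 10 days |
| Day 6 | Day 15 | Day 6 | 9 days |
| Day 7 or later | Day 6 | Day 6 | 0 |

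With the ±2-day window, the 9-day difference is 7 to 11 days. If Visit 2 is missed, the Day 6 discharge is dated Day 29, which is 23 days late. Censoring as not improved arises only if the Day 15 and Day 29 scores are both missing.

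So the patients affected are mainly those with baseline 4 who leave on the day oxygen stops or the day after. A baseline-5 patient who steps down to a recorded 4 in hospital is dated correctly.

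**Step 2: how common discharge is.** SAP Table 2 puts 36 + 37 = 73% of SOC and 31.90 + 50.70 = 82.6% of treated patients out of hospital at Day 15. With 50 per arm that is 36.5 and 41.3 patients. The share who leave within a day of stopping oxygen is not given. Call it f, as a share of all improvers before Day 15. The values 20%, 40% and 60% below are assumptions.

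**Step 3: effect on the SOC median.** Assume exponential times with 73% improved over the 14 days to Day 15. The daily rate is −ln(0.27)/14 = 0.0935. The elapsed time t at which half are recorded as improved solves (1 − f)(1 − e^(−0.0935t)) = 0.5. Add 1 for the study day and round up.
- f = 0: t = 0.693/0.0935 = 7.4, Day 9.
- f = 20%: t = −ln(0.375)/0.0935 = 10.5, Day 12.
- f = 40% or 60%: half is not reached before Visit 2, so Day 15. This happens once f exceeds 1 − 0.5/0.73 = 31.5%.

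Discharge is a stand-in here, because category 3 also counts as improvement from baseline 4. With categories 1 to 3 (17 + 36 + 37 = 90%), the rate is −ln(0.10)/14 = 0.1645. The SOC median then moves from Day 6 (t = 4.2) to Day 7 (t = 6.0), Day 12 (t = 10.9) and Day 15.

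**Step 4: effect on the hazard ratio and power.** These are simulations with 50 per arm, an unadjusted two-sided 5% Cox test and follow-up to Day 15 (1,500 trials per setting with Breslow ties, 500 with Efron). The true hazard ratio of 1.33 is ln(0.1745)/ln(0.27), where 0.1745 is the treated share still in hospital or dead under an odds ratio of 1.75.

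| f | HR, Breslow | Power, Breslow | HR, Efron | Power, Efron | Power at true HR 1.8, Breslow | Power at true HR 1.8, Efron |
|---|---|---|---|---|---|---|
| 0 | 1.32 | 21% | 1.33 | 25% | 70% | 75% |
| 20% | 1.28 | 17% | 1.28 | 19% | 55% | 64% |
| 40% | 1.23 | 10% | 1.29 | 19% | 34% | 58% |
| 60% | 1.19 | 5% | 1.29 | 17% | 21% | 54% |

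A separate simulation followed patients to Day 29, with an assumed underlying SOC median of 7 days, a true hazard ratio of 1.5 and Efron ties. It estimated 1.49, 1.43 and 1.46 at shares of 10%, 30% and 50%. The SOC median there moved from about 8.5 days to 9.7, 13.0 and 14.9. The median shift is therefore the stable finding, and the loss in the Cox analysis depends on the tie method.

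**The case against.** The strongest reply is that the SAP never says discharge is excluded. Categories 1 and 2 mean not hospitalized, so a programmer could treat the discharge date as the date of improvement, and the censoring rule applies only to patients who did not improve. A reader might infer that the plan rules discharge out; the text does not go that far. What stands is that 11.4.1 has no discharge rule, SAP 3.3 points to recorded scores, and 11.5.1 names discharge where it is meant to count. In an open-label trial the choice should not be left to programming.

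Second, Protocol 7.3.2 and 7.4.4 also describe the scale as the status at the first assessment of the day, which conflicts with the worst-of-previous-day sentence. On the first-assessment reading, the Day 6 discharge could be scored 3 that morning, and the gap narrows to patients who leave on the day oxygen stops. A discharge-day score might also be filled in later. These points reduce the number affected but do not supply the missing rule.

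Third, a reader might infer that one missed Day 15 visit turns a quick recoverer into a non-improver. It does not: WHO-7 is scored again at Day 29, and Protocol 7.3.3 allows remote methods for both visits.

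Fourth, a reader might infer from the Breslow columns that the endpoint loses most of its power. That result rests on assumed shares, follow-up cut at Day 15, discharge standing in for improvement, and one tie method. With categories 1 to 3 as improvement, Table 2 implies 90% and 94.05% improved and a hazard ratio of only ln(0.0595)/ln(0.10) = 1.23. The documents do not support a single power figure.

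Finally, time to discharge and the discharge-or-NEWS endpoint already capture early discharge, so the signal is not lost to the trial. That limits the importance of the point.

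**Conclusion.** The point holds as a gap in one secondary endpoint. With the recorded-score reading and the worst-of-previous-day rule, a baseline-4 patient discharged on the day oxygen stops or the day after is dated about 9 to 10 days late in the worked example. The date moves to Day 29 if Visit 2 is missed, and the patient is censored only if both later scores are missing.

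The number of such patients is unknown. Under assumed shares of 20% to 60%, the SOC median moves from about Day 9 to Days 12 to 15, or from Day 6 to Days 7 to 15 if category 3 is counted as improvement. The effect on the hazard ratio and power is mild to substantial, depending on a tie method that SAP 11.3 does not state. The primary Day 15 analysis and the sample size are not affected. This is an improvement worth making because it costs almost nothing.

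**What to change.** In SAP 11.4.1, define the event date as the earlier of (a) the date of the first recorded WHO-7 score at least one category better than baseline and (b) the date of discharge alive. Add that a patient discharged alive is not censored as a non-improver.

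While editing, state the tie method for the Cox models in SAP 11.3, and say which of the two descriptions of the daily score in Protocol 7.3.2 and 7.4.4 governs the analysis.

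The cost is a sentence or two in the SAP and about one line of programming. No new data are needed, because SAP 11.5.1 and 11.8.2 already use the discharge date. The change should be made before the analysis.

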11.4.2 WHO-7 Ordinal scale by timepoint

Descriptive statistics treating WHO-7 scale as continuous data in accordance to [section 3.1](#) will be reported for each treatment arm and overall at Baseline, Day 3, 5, 8, 11, 15 and 29. Change from baseline descriptive statistics will also be given for these timepoints for each treatment arm and overall. P-values and 95% CI comparing the differences between SOC and treatment arms A and B will also be provided for change from baseline analysis using a mixed model with baseline, treatment arm, age, day, site, interaction between day and treatment arm as fixed effects and patients as random effects with random intercepts using unstructured covariance structure. In the event of non-convergence, a simplified covariance structure may be chosen.

```
Proc Mixed data = adef;
class site trt subjid day;
model chg_bl = baseline site trt age day trt*day/ddfm=kr;
random int/sub= subjid type= un;
LSMEANS Trt*day / AT MEANS CL DIFF SLICE = day;
run;
```

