#### 7.4.4 Clinical support status

Patients will be assessed for their measures of clinical support, including:

- Hospitalized
- Oxygen requirement
- Non-invasive mechanical ventilation (via mask)
- Mechanical ventilator requirement (via endotracheal tube or tracheostomy tube)
- ECMO requirement
- Ordinal Scale Assessment
  - The ordinal scale is an assessment of the clinical status at the first assessment of a given study day. Each day, the worse score for the previous day will be recorded. i.e. on Day 3, Day 2 score is obtained and recorded as Day 2.
  - For the purposes of baseline the worse score from the previous day (Day -1) will be used
  - The scale is as follows:
    1. Not hospitalized, no limitations on activities
    2. Not hospitalized, limitation on activities
    3. Hospitalized, not requiring supplemental oxygen
    4. Hospitalized, requiring supplemental oxygen
    5. Hospitalized, on non-invasive ventilation or high flow oxygen devices
    6. Hospitalized, on invasive mechanical ventilation or ECMO
    7. Death

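### SAP 11.4.2 leaves discharged patients unscored on Days 3–11 and fits compound symmetry where it says unstructured, so its early WHO-7 contrasts are distorted and its by-day tests miscalibrated

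*SAP*

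**What the plan says.** **Model.** SAP 11.4.2 says that descriptive statistics "will be reported for each treatment arm and overall at Baseline, Day 3, 5, 8, 11, 15 and 29". It adds p-values and 95% CIs for Arms A and B against SOC on change from baseline. These come from a mixed model with baseline, arm, age, day, site and arm-by-day, and "patients as random effects with random intercepts using unstructured covariance structure". The code line is "random int/sub= subjid type= un", with Kenward-Roger degrees of freedom and no REPEATED statement. The fallback reads: "In the event of non-convergence, a simplified covariance structure may be chosen".

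**Data.** Protocol 7.3.2, which covers the ordinal scale on Days 2–14, opens with "At each study day while hospitalized, the following data will be collected". Protocol Table 3, footnote b, adds: "If patient is discharged prior to Day 14, the next visit should be Visit 2". SAP 2.3.2 lists the endpoint as "Status on an ordinal scale assessed daily while hospitalized and on days 15 and 28" (Day 28 there but Day 29 in 11.4.2, which should be reconciled).

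**Missing values.** SAP 3.3 imputes nothing unless stated. The one stated WHO-7 rule, in SAP 11.1, carries death forward as 7, and its example covers Days 11, 15 and 29. Discharge has no matching rule.

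**Purpose.** SAP 2.1 says Phase 2b will evaluate different days and numbers of categories of the scale. Protocol 10.3 lists the Day 15 timing among the features to be reassessed for Phase 3.

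**The concern.** No single sentence says that discharged patients lack a Day 3–11 score, but the collection, visit and missing-data rules together leave no source for one. The worst outcome is then always scored and the best two drop out. A mixed model that assumes data are missing at random cannot repair this, because whether the score is missing depends on the unseen score itself.

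Separately, the word unstructured has no content for one random intercept. The model assumes one variance for every day and one correlation for every pair of days. The fallback has nothing left to simplify.

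SAP 11.4.2 is the only planned inferential comparison of arms on WHO-7 away from Day 15. Anyone who uses it to compare days would see weakened early contrasts beside an over-significant Day 15.

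**Working it through.** **1. The plan's own figure.** The only powered figure is 462 for Phase 3; none is given for 11.4.2. Proportional-odds formula: n per arm = 6(z₀.₉₇₅ + z₀.₉₀)² / [(log OR)²(1 − Σp̄³)], where p̄ is the mean of the two Table 2 columns. Numerator: 6 × (1.960 + 1.2816)² = 63.04. Σp̄³ = 0.1264. Denominator: 0.5596² × 0.8736 = 0.2736. Result: 230.4, so 231 per arm and 462 in total; 462/0.9 = 513.3, so 514. The plan's figure is reproduced, and Table 2 is a sound base for what follows.

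**2. What the collection rule does, on Table 2.** Suppose Day 15 were collected as Days 3–11 are. The treatment column sums to 99.88 and is normalized.

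| Scoring | SOC mean | Treatment mean | Difference |
|---|---|---|---|
| All seven categories | 2.100 | 1.7757/0.9988 = 1.778 | −0.322 |
| Hospitalized or dead only | 1.01/0.27 = 3.741 | 0.6307/0.1728 = 3.650 | −0.091 |
| Discharged scored 2 | 1.46 + 1.01 = 2.470 | (1.652 + 0.6307)/0.9988 = 2.285 | −0.185 |
| Discharged scored 1 | 0.73 + 1.01 = 1.740 | (0.826 + 0.6307)/0.9988 = 1.458 | −0.282 |

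Collected that way, 0.091/0.322 = 28% of the difference remains.

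**3. Covariance.** With a random intercept of variance σ_b² and residual variance σ_e², Var(Y_day) = σ_b² + σ_e² on every day and Cov(Y_day, Y_day′) = σ_b² for every pair. That is compound symmetry.

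**4. One worked course.** The documents give no discharge rate before Day 15, so this course is assumed. It is a daily seven-state Markov model with patient frailty, fitted to Table 2 SOC at Day 15. Baseline 4/5 split is 75/25, with three arms of 50, five sites and no other dropout. There were 3,000 null runs; effect runs numbered 800, or 1,500 for the score-2 rows. The plan's model was fitted by REML with a t reference in place of Kenward-Roger. Full-score and score-2 rows use a separate ANCOVA for each day.

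| Day | 3 | 5 | 8 | 11 | 15 | 29 |
|---|---|---|---|---|---|---|
| Share scored (null) | 94% | 78% | 56% | 40% | 100% | 100% |
| Variance of change, full scores | 0.45 | 0.83 | 1.18 | 1.34 | 1.40 | 1.27 |
| Null rejection, as planned (%) | 0.3 | 0.9 | 1.3 | 1.6 | 12.5 | 10.4 |
| Null rejection, score 2 and own variance per day (%) | 4.3 | 4.3 | 4.4 | 4.6 | 4.7 | 5.1 |
| All improvement steps ×1.37: full scores | −0.148 | −0.253 | −0.318 | −0.326 | −0.310 | −0.205 |
| – as planned | −0.097 | −0.119 | −0.129 | −0.135 | −0.311 | −0.205 |
| – score 2 | −0.144 | −0.221 | −0.228 | −0.201 | −0.303 | −0.193 |
| Discharge step only ×1.8: full scores | −0.036 | −0.107 | −0.160 | −0.155 | −0.141 | −0.081 |
| – as planned | +0.017 | +0.030 | +0.035 | +0.047 | −0.140 | −0.081 |
| – score 2 | −0.030 | −0.084 | −0.111 | −0.098 | −0.134 | −0.069 |

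Effect kept as planned when all steps are faster: 0.129/0.318 = 41% on Day 8 and 0.135/0.326 = 41% on Day 11. The Day 15 error rate can be checked by hand. The empirical SD is 1.28 times the model SE, and 2[1 − Φ(1.96/1.28)] = 12.6%, against 12.5% simulated.

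**5. Other assumed courses.** These put 40–65% of SOC out of hospital by Day 11, used other baseline splits, or were more severe (4.6% dead by Day 15).

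- All improvement steps faster: 31–56% of the effect kept on Days 8 and 11.
- Discharge step only: about 0.00 to +0.04 as planned, against true values of −0.09 to −0.21.
- Worsening prevented only: 93–100% kept on Day 8 and 100–121% on Day 11.
- Null rejection as planned: 0.0–4.3% on Days 3–11, 10.3–14% on Day 15, 4.1–14.7% on Day 29.

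**6. Which change repairs what.** Four of those courses were refitted with each change. Unstructured covariance alone brings null rejection to 4.0–6.2% on all days but keeps only 39–61% of the Day 11 effect. Score 2 alone leaves Day 15 rejection at 9.3–11.5%. Both together give 4.2–6.1% on all days. Both are needed.

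**The case against.** This is a secondary analysis in a pilot that SAP 11.1 calls exploratory. Faster discharge is tested elsewhere, with death as a competing risk, in SAP 11.8.2 and 11.5.1; time to first improvement is in 11.4.1. The evaluation of days in SAP 2.1 is by severity and number of categories, and 11.4.2 contains neither. Every size above rests on an assumed course, and scoring discharge as 2 is itself an assumption.

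Most of this stands, and it limits the point to a secondary analysis. It does not remove it: the other analyses do not compare days of the scale, and both defects follow from the text without simulation.

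Four stronger readings are tempting, and the documents do not support them.

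- A reader might infer that any benefit is simply shrunk. That depends on the mechanism: faster discharge alone can reverse the sign, and prevention of worsening loses little.
- A reader might infer that the 11.4.2 p-values choose the Phase 3 day. No text says so.
- A reader might infer that Day 29 is always over-rejected. In one course it was 4.1%.
- A reader might infer that the primary result is compromised. It is a separate Day 15 proportional-odds model, and carrying death forward is sound there.

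**Conclusion.** Both defects hold as the plan is written. Under (a), the Day 3–11 contrasts are distorted, and the size and even the sign depend on how the drug acts. Under (b), the by-day tests do not hold their nominal level. Kenward-Roger degrees of freedom do not correct a wrong covariance structure.

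Two results held in every setting tried: distortion of the early contrasts when recovery is faster, and a Day 15 error rate at least twice nominal. The exact percentages rest on assumed daily transitions, baseline splits and discharge timing, and should be read as illustrations. Readmission and death after discharge were not simulated. The change is worth making before the Phase 2b analysis, at the weight of a secondary analysis.

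**What to change.** In SAP 11.4.2:

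1. **Covariance.** Replace the RANDOM line with `repeated day / subject=subjid type=un;` and keep `ddfm=kr`. Reword the sentence to unstructured covariance over days. Name the fallback order: heterogeneous Toeplitz, then heterogeneous compound symmetry.
2. **Discharge.** Make one analysis the main one. A patient discharged alive is scored 2 on each scheduled Day 3, 5, 8 or 11 after the day of discharge and before Visit 2. The day of discharge keeps its in-hospital score if one was recorded; Protocol 7.4.4 says "Each day, the worse score for the previous day will be recorded", so it may not have been. Death (7) takes precedence. Recorded scores are used after a readmission. No score is assigned after withdrawal or loss to follow-up.
3. **Sensitivity.** Report score 1 and the as-collected data as two sensitivity analyses, without claiming that they bracket the true effect.

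The cost is a paragraph of text, one line of code and the sensitivity tables. The discharge date is already needed for SAP 11.8.2. The downside is that categories 1 and 2 cannot be told apart for discharged patients on Days 3–11. Score 2 therefore misses part of the effect: with all improvement steps faster, about 65–75% is kept on Day 11 in most courses, and 0.201/0.326 = 62% in the one tabulated. Score 1 may overstate it.
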